#### **Amputation:**

**Major Unplanned Amputation:** Surgical removal of a limb or a part of a limb above the metatarsal line where prosthesis is required for standing or walking, that was unanticipated prior to the index procedure.

**Minor Amputation:** Surgical removal of toes at or below metatarsus preserving functionality of foot.

**Aneurysm:** A localized, pathological, blood-filled dilatation of a blood vessel caused by a weakening of the vessel wall.

Ankle-Brachial Index (ABI): The ratio of the highest ankle systolic pressure to the highest brachial systolic pressure.

Artery Dissection: Intimal disruption of the vessel wall with or without medial or adventitial contrast staining. See also National Heart, Lung and Blood Institute (NHLBI) Classification of Dissection.

**Artery Perforation:** Identifiable by extravasation of contrast media outside the arterial adventitial space.

Artery Rupture: Large transmural disruption of a vessel with gross extravasation and hemorrhage.

Arterio-venous (AV) Fistula: A communication between an artery and a vein in which the arterial blood flows directly into a neighboring vein.

**Bleeding:** Blood loss resulting from the percutaneous interventional procedure or adjunctive drug therapy that may require transfusion of blood products.

Chronic Renal Insufficiency: Dialysis dependent, or eGFR < 30 ml/min or creatinine >2.5.

**Clinically Significant Distal Embolism:** A clinically relevant obstruction of a blood vessel by a foreign substance (plaque or debris) or a blood clot that requires further mechanical or pharmacologic treatment besides vasodilators. Clinical relevance is determined either by a surgical or medical intervention and/or the presence of symptoms (i.e. decreased ABI, symptomatic claudication, etc).

**Compressible Artery:** An artery without significant calcification that can be evaluated by duplex ultrasound or an artery that results in an ABI value < 1.3.

Death: The termination of life.

**Device Outcome:** Categorized by < 50% residual stenosis following JS atherectomy alone and without additional adjunctive PTA or bail out procedures as determined by the Angiographic Core Laboratory.

**Diabetes (History of):** Defined as patients who have been diagnosed with either Type I or Type II diabetes and are currently taking oral hypoglycemics or insulin or have a hemoglobin A1C > 7%.

**Discharge:** The time point when the subject is released from the admitting hospital, transferred to another facility, or has expired.

**Distal Embolization:** Migration of air, plaque, thrombus, or debris that occludes the distal target vessel or one of its branches.

**Embolism:** Obstruction of a blood vessel by a foreign substance (air, plaque, debris) or a blood clot.

**Emergent Surgical Revascularization:** Surgery performed on an urgent or emergent basis as a result of the PTA procedure and/or use of a study device.

**Enrollment:** The subject is enrolled in the study after he/she has signed the patient informed consent and has been determined to meet all inclusion and none of the exclusion criteria. The point of enrollment is defined as the moment an exchangeable guidewire and treatment catheter cross the target lesion in the true lumen.

Fever: An increase in internal body temperature to levels that are above normal (37°C, 98.6°F).

**Gastrointestinal (GI) bleeding:** any bleeding that starts in the gastrointestinal tract, which may extend from the mouth to the anus.

**Hematoma:** Localized mass of extravasated blood  $\geq 5$  cm that prolongs hospitalization.

Hemorrhage: Bleeding requiring hospitalization, repeat procedure, operation or transfusion.

**Hypertension:** Increase in systolic blood pressure above 140 mm Hg or a diastolic blood pressure above 90 mm Hg.

**Hypotension:** Fall in systolic blood pressure that requires intravenous treatment with vasopressors or inotropic agents.

**Index Procedure:** The procedure in which the subject has the study procedure performed or attempted.

Index Lesion: The target lesion treated during the index procedure

**Infection:** Inflammation caused by bacterial or viral sources, such as, urinary tract infection, puncture site infection, sepsis, endocarditis, and bacteremia from IV site.

**Inflammation:** An immunologic response to infection or trauma that can result in localized redness, swelling, heat, pain and dysfunction of the organs involved.

Inflow Tract: Vascular access point to the area of the target lesion.

Intraluminal thrombus: A blood clot within a vessel.

**Intimal Flap:** Superficial dissection of the vessel that does not result in medial or adventitial contrast staining (NHLBI Type A dissection).

**Invasive Assessment/Procedure:** Any assessment, intervention or therapy that penetrates the skin, excluding administration of parenteral fluids or drugs.

**Ischemia:** a restriction in arterial blood flow by stenosis, restenosis or occlusion that, if prolonged, can lead to tissue damage.

**JS pass:** Movement of the JS across the target area. One pass is the movement of the JS from the proximal to the distal end of the lesion

**Major bleed by TIMI criteria:** Loss of more than 5 gm/dl of Hemoglobin or the need to transfuse 5 Units of blood or intracranial bleed

Minor Bleed by TIMI criteria: a bleed other than non TIMI major bleed

**Myocardial Infarction (Non-Q wave):** Post-treatment elevation of CK-MB more than 3 times the upper limit of lab normal value without evidence of pathologic Q-waves present on EKG. Elevated serum troponin levels are not sufficiently validated to be considered sole evidence of an MI in the absence of CK-MB elevations.

**Myocardial Infarction (Q wave):** Development/appearance of new pathological Q-waves in more than 2 contiguous leads per 12-lead electrocardiogram (EKG/ECG).

#### National Heart, Lung and Blood Institute (NHLBI) Classification of Dissection:

Dissection	Description
Type A	Small radiolucent area within the lumen of the vessel disappearing with
	the passage of contrast material
Type B	Appearance of contrast medium parallel to the lumen of the vessel
	disappearing within a few cardiac cycles
Type C	Dissection protruding outside the lumen of the vessel persisting after
	passage of the contrast material
Type D	Spiral shaped filling defect with delayed runoff of the contrast material

Dissection	Description
	in the distal vessel
Type E	Persistent luminal filling defect with delayed runoff of the contrast
	material in the distal vessel
Type F	Filling defect accompanied by total coronary occlusion

**Net Lumen:** The difference between the target lesion minimum lumen diameter at baseline and at follow-up per angiographic assessment.

Occlusion: An obstruction within an artery.

#### **Patency Classifications:**

- Patency via Duplex (Peak Systolic Velocity ≤ 2.5): Defined by duplex ultrasound measurement of peak systolic velocity (PSV) ratio ≤ 2.5 at the target lesion.
- **Patency via angiography:** Defined as < 50% stenosis per angiography as determined by the Angiographic Core Laboratory.
- Assisted primary Patency: Defined as < 50% stenosis per angiography or duplex as maintained by repeat percutaneous intervention of a non-occluded vessel
- Secondary Patency: Defined as < 50% stenosis per angiography or duplex, as maintained by repeat percutaneous intervention of a non-occluded or occluded vessel

**Percent Stenosis:** Native vessel diameter as measured at the most narrow point of the lesion divided by the estimated native vessel diameter (the mean of the vessel diameters proximal and distal to the lesion) at that location.

% Stenosis =  $\frac{Diameter \ at \ most \ narrow \ segment \ of \ lesion \ (mm)}{\left[\left(proximal \ vessel \ diameter \ + \ distal \ vessel \ diameter \right)/2\right]}$ 

**Physician-Directed Subject Withdrawal:** Withdrawal of a subject from the study at the direction of the Principal Investigator. Reasons for physician-directed subject withdrawal include, but are not exclusive to: the subject is not adhering to the Study Protocol requirements, the subject has enrolled in another study that conflicts with the JET-ISR outcomes of interest, or the physician deems it in the best interest for the safety or welfare of the subject to withdraw.

Pre-Procedure: The time until the procedure begins (before arterial access is obtained).

**Principal Investigator:** Physician responsible for overall clinical management of subjects enrolled at his/her institution. Assumes overall responsibility and accountability for the clinical team and for data obtained from each subject participating in the study. Ensures compliance with the Study Protocol, applicable laws, and applicable regulations; ensures informed consents are signed, and reviews and signs eCRF indicating documents are accurate and complete.

**Procedural Outcome:** Categorized by < 30% residual stenosis following the protocol-defined treatment (JS + PTA) with provisional or bail out procedures as determined by the Angiographic Core Laboratory.

**Procedural Success:** Defined as  $\leq$ 30% residual diameter stenosis following JS + PTA without provisional or bailout procedures.

Protocol Deviation: Any divergence from the Study Protocol.

Pseudoaneurysm: Perforation of the vessel with arterial blood flow outside of the vessel.

**Renal Failure:** Failure of the kidneys to perform essential functions that requires dialysis.

**Runoff Vessel:** An artery distal to treated vessel, including the popliteal, peroneal tibials and the dorsalis pedis.

**Rutherford Clinical Category:** A classification system of clinical categories of chronic limb ischemia ranging from 0 to 6. The categories and clinical descriptions are:

Category	Clinical Description
0	Asymptomaticno hemodynamically significant occlusive disease
1	Mild claudication
2	Moderate claudication
3	Severe claudication
4*	Ischemic rest pain
5*	Minor tissue loss—non-healing ulcer, focal gangrene with diffuse pedal ischemia
6*	Major tissue lossextending above TM level, functional foot no longer salvageable

\*Categories 4, 5, and 6 are embraced by the term chronic critical ischemia. †Five minutes at 2 mph on a 12% incline.

Sepsis: Systemic inflammatory response to infection.

**Severe or Moderate Calcification:** Grade 2 (moderate) or higher (severe) as defined by the Peripheral Arterial Calcium Scoring System (PACSS)

Proposed Fluoroscopy/DSA based Peripheral Arterial Calcification Scoring System (PACSS): Intimal and medial vessel wall calcification at the target lesion site as assessed by high intensity fluoroscopy and digital subtraction angiography (DSA) assessed in the AP projection.

Grade 0: No visible calcium at the target lesion site

Grade 1: unilateral calcification < 5cm; a) intimal calcification; b) medial calcification; c) mixed type

Grade 2: unilateral calcification ≥ 5cm; a) intimal calcification; b) medial calcification; c) mixed type

Grade 3: bilateral calcification < 5cm; a) intimal calcification; b) medial calcification; c) mixed type

**Grade 4:** bilateral calcification  $\ge$  5cm; a) intimal calcification; b) medial calcification; c) mixed type

Stenosis: An abnormal narrowing of an artery.

**Stroke:** Neurological dysfunction caused by a brain disturbance or ischemia, with clinical symptoms lasting >24 hours or imaging of an acute clinically relevant brain lesion in patients with rapidly vanishing symptoms.

**Study Coordinator:** Employee at study site who assists Principal Investigator with study activities as delegated by the Principal Investigator, including tracking subjects involved in the study, scheduling testing and follow-up visits, maintaining study records, completing and providing eCRFs to the Sponsor in a timely manner.

**Sub-acute Closure:** Vessel occlusion at the site of treatment between 24 hours and 4 weeks after successful index procedure.

**Sub-Investigator(s)**: Physician(s) responsible for study activities in coordination with Principal Investigator and in accordance to the Study Protocol.

**Systemic Infection:** the bloodstream infection that affects a number of organs and/or tissues, or affects the body as a whole.

**Target Lesion:** The lesion meeting all of the angiographic inclusion criteria and none of the exclusion criteria is the target lesion. Only one target lesion is allowed per subject.

**Target Lesion Revascularization (TLR) at 6 months**: TLR is defined as retreatment of the index lesion (extended 1 cm proximal and distal to the lesion) at 6 months. For the primary endpoint, intra-procedural bail out stenting of the index lesion is considered meeting a TLR endpoint. (ITT analysis).

**Target Lesion Revascularization (TLR) at 6 months**: TLR is defined as retreatment of the index lesion (extended 1 cm proximal and distal to the lesion) at 6 months. For the secondary endpoint, Intra-procedural bail out stenting of the index lesion is NOT considered meeting a TLR endpoint. (ITT analysis)

**Target Lesion Revascularization (TLR) at 1 year**: TLR is defined as retreatment of the index lesion (extended 1 cm proximal and distal to the lesion) at 1 year

ITT (bail out stent in the Lab is considered as TLR) ITT (bail out stent in the Lab is not considered as TLR)

**Target Lesion Patency at 6 months and 1 year:** Defined as  $PSVR \le 2.5$  at the treated site or < 50% stenosis by angiography as determined by the Angiographic Core Laboratory in the absence of TLR, amputation, and/or surgical bypass (the evaluation of patency is extended to one cm proximal and one cm distal to the target lesion)

	http://www.sirweb.org/clinical/cpg/TASC_guidelines.pdf		

**Transient Ischemic Attack (TIA):** Brief episode of neurological dysfunction caused by a focal disturbance of brain or retinal ischemia, with clinical symptoms typically lasting less than 1 hour, and without evidence of infarction.

Treatment interval: Time from JS activation until deactivation (via physician's hand control).

**Unanticipated or Unexpected Adverse Device Effect:** Any serious adverse effect on health or safety or any life-threatening problem or death caused by, or associated with, a device, if that effect, problem, or death was not previously identified in nature, severity, or degree of incidence in the protocol or application (including a supplementary plan or application), or any other unanticipated serious problem associated with a device that relates to the rights, safety, or welfare of subjects.

Vessel Spasm: A sudden, brief tightening of a blood vessel.

•

#### Appendix A JET ISR

#### **Meta-analysis**

We completed a meta-analysis for the 3 randomized trials published (1-3) with femoropopliteal in-stent restenosis where the control arm was balloon angioplasty alone. Below is a table of this meta-analysis. This showed that TLR with balloon angioplasty alone was 37.9%.

#### Estimated Counts of TLR with Bailout Stenting at 6-Months

Estimated Counts of TLR with Bailout Stenting at 6-Months				
Author, year	Treatment	Control	Total	
Boisers et al., 2015	(2/39) 5.3%	(15/44) 34.2%	(17/83) 20.5%	
Krankenberg et al., 2015	(3/62) 5.2%	(15/57) 26.0%	(18/119) 15.1%	
Dipple et al., 2015	(45/169) 26.5%	(39/81) 48.2%	(84/250) 33.6%	
Total	(50/270) 18.5%	(69/182) 37.9%	(119/452) 26.3%	

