# Study Protocol Synopsis

JET-ISR trial				
Protocol Number	MCRF-S002-2015			
Devices	JetStream Navitus XC 2.1 and 2.4			
Primary Purpose	The purpose of this study is to test the hypothesis that Jetstream atherectomy and adjunctive balloon angioplasty (JS +PTA) improves target lesion revascularization (TLR) at 6 months follow-up when compared to historic data from balloon angioplasty alone (PTA) in the treatment of femoropopliteal arterial In-stent restenotic (ISR) disease			
Study Design	A prospective, multicenter, single arm study evaluating the investigational use of Jetstream Atherectomy (JS) and adjunctive balloon angioplasty (JS +PTA) in the treatment of femoropopliteal ISR lesions in subjects with claudication or limb ischemia (Rutherford clinical category (RCC) of 2-4) (lesion length $\geq$ 4 cm). The comparator arm is historic data from plain old balloon angioplasty derived from a Meta-analysis of the 3 published randomized trials in the field.			
Follow-Up	Follow-up assessments will occur at pre-discharge, 30 days, 6 months and			
Schedule	I year following the study procedure.			
	Assumptions: TLR with bailout stenting from historic control from meta-analysis: 37.9% TLR with bailout stenting from Jetstream ISR feasibility study: 20.7% Power 80% Alpha 0.05			
Statistical assumption and analysis	We are planning a study of independent cases and controls with 1 control(s) per case. Prior data indicate that the failure rate among controls is 0.38. If the true failure rate for experimental subjects is 0.21, we will need to study 112 experimental subjects and 112 control subjects to be able to reject the null hypothesis that the failure rates for experimental and control subjects are equal with probability (power) 0.8 (meta-analysis from published randomized trials provides data on 182 controls). The Type I error probability associated with this test of this null hypothesis is 0.05. We will use an uncorrected chi-squared statistic to evaluate this null hypothesis. Assumingly a loss of 20% of patients on follow-up a minimum of 134 patients will be enrolled.			
Number of Sites	Up to 14 sites in the USA			

Primary Outcomes	Effectiveness: Target Lesion Revascularization (TLR) at 6 months : TLR is defined as retreatment of the index lesion (extended 1 cm proximal and distal to the lesion) at 6 months. For the primary endpoint, intra-procedural bail out stenting of the index lesion is considered meeting a TLR endpoint. (ITT analysis)		

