Recently 3 randomized trials were presented in treating FP ISR; the EXCITE ISR trial (randomized laser + PTA vs PTA alone), the RELINE trial (randomized Viabahn stent vs PTA) and the Randomized Femoral Artery In-Stent Restenosis (FAIR) Trial.. In the GORE VIABAHN (W.L Gore and Associates, Newark, Delaware, USA) Versus Plain Old Balloon Angioplasty (PTA) for Superficial Femoral Artery (SFA) In-Stent Restenosis (RELINE) trial, Viabhan endograft stent was shown to be superior to PTA leading to significantly better patency rates at 1 year (37% versus 74.8% respectively). In the EXCImer Laser Randomized Controlled Study for Treatment of FemoropopliTEal In-Stent Restenosis (EXCITE ISR) trial, a multicenter, prospective, randomized, controlled trial conducted across 40 U.S. centers. A total of 169 ELA + PTA subjects (62.7% male; mean age  $68.5 \pm 9.8$  years) and 81 PTA patients (61.7% male; mean age  $67.8 \pm 10.3$  years) were enrolled. Mean lesion length was  $19.6 \pm 12.0$  cm versus  $19.3 \pm 11.9$  cm, and 30.5% versus 36.8% of patients exhibited total occlusion. ELA + PTA subjects demonstrated superior procedural success (93.5% vs. 82.7%; p = 0.01) with significantly fewer procedural complications. ELA + PTA and PTA subject 6month freedom from TLR was 73.5% versus 51.8% (p < 0.005), and 30-day major adverse event rates were 5.8% versus 20.5% (p < 0.001), respectively. ELA + PTA was associated with a 52% reduction in TLR (hazard ratio: 0.48; 95% confidence interval: 0.31 to 0.74). This trial showed that debulking with the laser is an important strategy to reduce TLR in treating FP ISR when compared to PTA. Finally, The Randomized Femoral Artery In-Stent Restenosis (FAIR) Trial, randomized 119 patients with superficial femoral artery in-stent restenosis to drug coated balloon (DCB) (n=62) versus PTA (n=57). Mean lesion length was 82.2±68.4 mm. and 28.6% of lesions were totally occluded. The primary end point of recurrent in-stent restenosis assessed by ultrasound at 6 months was 15.4% (8 of 52) in the DCB and 44.7% (21 of 47) in the PTA group (P=0.002). Freedom from target lesion revascularization was 96.4% versus 81.0% (P=0.0117) at 6 months and 90.8% versus 52.6% (P<0.0001) at 12 months, respectively. No major amputation was needed. Two patients in the DCB and 3 patients in the PTA group died. No death was procedure related.

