### 4.2 PRIMARY OUTCOME

### Effectiveness

**Target Lesion Revascularization (TLR) at 6 months**: TLR is defined as retreatment of the index lesion (extended 1 cm proximal and distal to the lesion) at 6 months. For the primary endpoint, intra-procedural bail out stenting of the index lesion is considered meeting a TLR endpoint. (Intention to treat Analysis analysis)

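### Appendix A combines bailout stenting with TLR differently across the three PTA arms, so the 37.9% control rate is not shown to match the JET-ISR primary outcome

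*Combined protocol and SAP*

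**What the plan says.** Section 4.2 defines the effectiveness outcome as TLR at 6 months and adds: "For the primary endpoint, intra-procedural bail out stenting of the index lesion is considered meeting a TLR endpoint". A patient therefore counts once, whether the event is a bailout stent, a later retreatment, or both.

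The comparator is historical. The Synopsis lists "TLR with bailout stenting from historic control from meta-analysis: 37.9" per cent, and Section 5.25 tests JetStream against that rate. Its source is the Appendix A table headed "Estimated Counts of TLR with Bailout Stenting at 6-Months", whose control column reads 15/44 (34.2%) for the stent-graft trial, 15/57 (26.0%) for the drug-coated-balloon trial and 39/81 (48.2%) for the laser trial, total 69/182. The text introducing that table leaves bailout out of the label: "This showed that TLR with balloon angioplasty alone was 37.9" per cent.

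Section 3.2 gives 6-month results for two of the three trials. For the drug-coated-balloon trial: "Freedom from target lesion revascularization was 96.4% versus 81.0% (P=0.0117) at 6 months", drug-coated balloon first. For the laser trial: "ELA + PTA and PTA subject 6month freedom from TLR was 73.5% versus 51.8% (p < 0.005". For the stent-graft trial it gives only 1-year patency. The DSMB row of the Synopsis puts bailout in the PTA control arms at 7 to 20%.

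**The concern.** All three rows stand under one heading, but two of them relate differently to the TLR rates the protocol itself reports. One was raised; the other was carried over unchanged. Appendix A gives no TLR-only column, no bailout column, no source definition of TLR and no rule for patients who had both events.

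This matters because 69/182 is the fixed side of the only efficacy test. Summing TLR and bailout double-counts any patient with both, which overstates the control rate and favours JetStream. Leaving bailout out of an arm understates the rate and works against JetStream. A result near the boundary could turn on this bookkeeping.

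**Working it through.** **1. The plan's own figures.** Pooled control: (15 + 15 + 39)/(44 + 57 + 81) = 69/182 = 37.9%. Sample size for 0.38 v 0.21 (two-sided 0.05, 80% power, 1:1, no continuity correction), with mean proportion 0.295:

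n = [1.960 × √(2 × 0.295 × 0.705) + 0.842 × √(0.38 × 0.62 + 0.21 × 0.79)]² / 0.17² = 111.8, so 112 per group. Both figures reproduce.

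**2. Appendix A against Section 3.2.** Implied TLR is 100 minus freedom from TLR.

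| Trial and arm | Implied TLR | Appendix A | Gap |
|---|---|---|---|
| Drug-coated balloon, PTA | 100 − 81.0 = 19.0% | 26.0% | 7.0 points; 4/57 = 7.0% |
| Drug-coated balloon, treated | 100 − 96.4 = 3.6% | 5.2% | 1.6 points; 1/62 = 1.6% |
| Laser, PTA | 100 − 51.8 = 48.2% | 48.2% | 0 |
| Laser, treated | 100 − 73.5 = 26.5% | 26.5% | 0 |
| Stent-graft, PTA | not given | 34.2% | not traceable |

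The first two gaps correspond to whole patients, and 7% is the lower end of the Synopsis bailout range. A bailout percentage added to TLR is the natural reading, though the documents do not state it. The laser arm supplies 39 of the 69 control events (57%).

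**3. Overlap in the drug-coated-balloon PTA arm.** TLR is 0.19 × 57 = 10.8, about 11 patients; presumed bailout is 4.
- No overlap: 15/57, pooled 69/182 = 37.9%.
- Independence: expected overlap 4 × 0.19 = 0.8, so about 14/57, pooled 68/182 = 37.4%.
- Full overlap: 11/57, pooled 65/182 = 35.7%.

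**4. If the laser figure omits bailout (assumption: 7 to 20%, from the Synopsis).**
- Full overlap: 39/81, pooled 69/182 = 37.9%.
- Independence: 48.2 + 0.518 × 7 = 51.8% (42/81), pooled 72/182 = 39.6%; 48.2 + 0.518 × 20 = 58.6% (47/81), pooled 77/182 = 42.3%.
- No overlap: 55.2% (45/81), pooled 75/182 = 41.2%; 68.2% (55/81), pooled 85/182 = 46.7%.

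**5. Effect on the test.** Highest JetStream count out of 112 that is significantly lower than control (uncorrected chi-squared, two-sided 0.05, all 182 controls used):

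| Control | Highest significant count | p at that count |
|---|---|---|
| 65/182 | 27 | 0.037 |
| 68/182 | 29 | 0.042 |
| 69/182 | 30 | 0.04995 |
| 75/182 | 33 | 0.043 |
| 85/182 | 39 | 0.045 |

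With 28 JetStream events, p = 0.022 against 69/182 and 0.055 against 65/182.

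**The case against.** A reader might infer from step 2 that the 37.9% pools different endpoints, or that it is inflated in the device's favour. The documents support neither. They do not give the laser trial's definition of TLR. If it already counted bailout, leaving 48.2% unchanged while raising the drug-coated-balloon arm is correct harmonisation. The heading over all three rows claims as much. Section 3.2 also reports, for the laser trial, "30-day major adverse event rates were 5.8% versus 20.5% (p < 0.001), respectively"; the higher figure, in the PTA arm, is compatible with bailout being counted but does not prove it.

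The overlap effect may also be small. Full overlap needs all four presumed bailout patients to have had a later TLR. Independence moves the pooled rate by about half a point and the boundary by one event. At the planned 21%, about 0.21 × 112 = 23.5 JetStream events are expected, below even the lowest boundary of 27. With the 182 controls held fixed, the chance of significance is 94% against 69/182 and 82% against 65/182.

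These points stand. They rule out calling the comparator wrong, and they show that the plan does not collapse at its planning rate. They do not supply the missing derivation. Nor do they protect a JetStream result of 28 to 30 events, which is significant against 69/182 but not against 65/182.

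**Conclusion.** The 37.9% reproduces arithmetically, but it is not shown to be the JET-ISR primary outcome in PTA patients. One row appears to be an unadjusted sum. One is right only under a source definition that the documents do not give. One cannot be traced.

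Overlap in the drug-coated-balloon arm alone puts the pooled rate at 35.7% to 37.9% (about 37.4% under independence) and the significance boundary at 27 to 30 of 112. This assumes that the 7.0-point gap is bailout. If the laser figure omits bailout at an assumed 7 to 20%, the pooled rate is 37.9% to about 47% and the boundary 30 to 39; the present comparator would then be too low and work against JetStream. The two possible errors have opposite signs, so the net direction is unknown. No range can be given for the stent-graft row. The point goes beyond missing detail, because the resolution could change the efficacy conclusion.

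**What to change.** Before JetStream outcomes are analysed:

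- Re-extract each PTA arm from the three source papers. Tabulate TLR alone, bailout alone, the combined per-patient count, and whether the source TLR already includes bailout.
- Restate the pooled control rate on the JET-ISR definition, and label it the same way in the Synopsis, Section 5 and Appendix A.
- Where overlap is unpublished, report the primary test across the overlap bounds, from the larger of the two components to their simple sum, as a prespecified sensitivity analysis. The full-overlap bound should not become the primary comparator: that would replace one extreme assumption with the opposite one.
- Compare the bailout-free 6-month TLR (secondary outcome 4 in Section 4.3) only with TLR-alone control rates, where these are available.

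The cost is some re-extraction from papers the plan already cites, and a control rate that may move in either direction. If the laser trial did count bailout, one sentence and its source settle that row.
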